7. STATISTICS AND DATA ANALYSIS

There will be three trial arms in this RCT. Based upon previous studies, and what would constitute a clinically meaningful effect size a power calculation has been conducted (18). Assuming 5% type 1 error probability, 80% power, and an effect size of 3%, results in a minimum sample size of 2797 people per study arm (8391 in total). Chi-squared non-parametric statistic will be used to determine whether effects are significant. Secondary outcomes will examine the impact upon attendance amongst subgroups including those with different invitation type and from different demographic groups. A regression model will be developed to test these secondary hypotheses.

Data flow for this project is demonstrated in **figure 2**.

Figure 2 Demonstrating data flow of project.

Variables that will be extracted for analysis will include:

1. Demographics
 - Age at invitation
 - Index of Multiple Deprivation (derived from postcode)
 - Ethnicity
 - Previous attendee/non-attendee/first-time invitee
2. Invitation
 - Invitation type (open or timed)
 - Screening service location
3. Outcome
 - Attendance at booked appointment

Data and all appropriate documentation will be stored for a minimum of 10 years after the completion of the study, including the follow-up period.

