4.3. EXCLUSION CRITERIA	9
4.4. WITHDRAWAL CRITERIA	9
5. ADVERSE EVENTS	9
5.1. DEFINITIONS	9
5.2. REPORTING PROCEDURES	10
6. ASSESSMENT AND FOLLOW-UP	10
7. STATISTICS AND DATA ANALYSIS	11
8. REGULATORY ISSUES	12
8.1. ETHICS APPROVAL	12
8.2. CONSENT	12
8.3. CONFIDENTIALITY	12
8.4. INDEMNITY	13
8.5. SPONSOR	13
8.6. FUNDING	13
8.7. AUDITS	13
9. STUDY MANAGEMENT	13
10. PUBLICATION POLICY	13
11. REFERENCES	13

GLOSSARY OF ABBREVIATIONS

BCT	Behavioural Change Technique
ICL	Imperial College London
NHS	National Health Service
NHSBSP	NHS Breast Screening Programme

NHSE	NHS England
RCT	Randomised Controlled Trial
SMS	Short Message Service

KEYWORDS

Breast cancer screening, uptake, behavioural science, SMS messaging

STUDY SUMMARY

TITLE Investigating the use of behavioural science informed messages to facilitate attendance at Breast Cancer Screening

DESIGN Randomised Controlled Trial

AIMS To determine the impact of SMS messages, and a video developed using behavioural science upon the uptake

[figure not shown]
OUTCOME MEASURES Primary: percentage uptake of the invitation to screen. Secondary: percentage uptake of the invitation to screen amongst population subgroups (e.g. by demographic factors, and by invitation type).

POPULATION All women aged between 50 and 70, invited to screen in the London breast cancer screening region.

ELIGIBILITY Eligible to attend the NHSBSP in London during the study period.

DURATION 6 months

REFERENCE DIAGRAM

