1. INTRODUCTION

1.1. BACKGROUND

Breast cancer is the most common cancer in the UK, with 1 in 8 women affected during their lifetime(1). Whilst survival rates are high, the 5-year survival rate is 72% higher with the earliest stage breast cancer, compared to the latest disease stage(2). The NHS Breast Cancer Screening Programme (NHSBSP) invites women aged 50 to 70 years old every three years to a mammogram. By enabling earlier detection, it is estimated that the NHSBSP saves 1300 lives per year(3).

Despite the potential benefits of breast cancer screening, attendance is falling. Coverage rates have fallen nationally by 1.3% between 2016 and 2020. London has shown particularly poor rates (67.3%), with coverage in 2020 below the acceptable target of 70%(4). The COVID-19 pandemic has exacerbated these trends with an estimated 1 million mammograms missed, due to the cessation of screening to minimise transmission risk (5)(6). Counteracting these trends is a significant public health priority.

Furthermore, there is increasing concern regarding the socio-demographic inequalities in breast screening uptake. For example, the odds of attendance amongst those from the most

deprived areas is 5% lower than those from less deprived areas (7)(8). In addition, in one study in London, the adjusted odds of attendance were almost three times higher amongst White British, compared to Asian women, and six times higher than Black women(9). The barriers faced by these groups need to be appreciated, and any intervention to increase attendance ensure that inequalities are not widened(10).

Behavioural Science is a field of study concerning understanding the processes underpinning human action(11). Behavioural theories, such as the Capability Opportunity Motivation-Behaviour (COM-B) model (12, 13), have been used to understand the determinants of several health behaviours including handwashing and smoking (14, 15). Recent studies have shown the application of behavioural science to screening may also facilitate uptake of invitations (16). In one study by Kerrison et al. the use of a reminder prompt SMS increased uptake by 5% (17). However, the use of plain text messages limits which behavioural determinants can be feasibly addressed, and what techniques can be used. Video messages can allow for more complex and a broader range of behavioural change techniques (BCTs) to be incorporated, and therefore have greater impact upon attendance.

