2. STUDY OBJECTIVES

The primary object is to determine the impact of behavioural science informed (1) video and (2) SMS messages compared to usual care, upon uptake of breast cancer screening. Secondary objectives involve how this impact on attendance differs between population subgroups including people from differing demographic groups and people invited to open, as opposed timed appointments (see Study Design).

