3. STUDY DESIGN

This study will be conducted as a randomised control trial (RCT) in the London screening region of the NHSBSP. The study will last over 6 months. The administrative hub for the NHSBSP in London is based at the Royal Free Hospital, who will oversee invitation scheduling, message delivery and outcome data collation through their existing delivery systems.

Participants will be randomised using simple randomisation method in a 1:1:1 fashion to either intervention arm or usual care. Randomisation will utilise a computerised system in which each participant who is due for screening in the study period is randomly allocated a

number corresponding to the message they will receive. This will be undertaken by the screening hub, and will be passed on to the message delivery service who will ensure the correct template is sent.

Written invitations are sent, as standard practice, by the NHSBSP to invite women to either (1) an appointment at a set time, date and location (so-called timed invitations) or (2) to call and book an appointment (or open invitation). Following this, as part of usual care, those selected for open invitations will receive a first SMS 7 days post written invitation. They will then receive two SMS reminders, 7 days and 2 days prior to the appointment, once it has been booked. Those who receive timed invitations will just receive the two reminder messages, 7 and 2 days prior to the appointment. The decision to offer an individual a timed or open invitation is made by the screening service based on their covid-19 recovery process, and will not be altered by this project.

This RCT will involve randomising participants to receive the usual care messages (according to the timings outlined above), a plain text SMS incorporating BCTs or the BCT SMS with a new link to a video incorporating more BCTs (see **figure 1 for message content in each of the three trial arms**).

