3.1. STUDY OUTCOME MEASURES

The primary outcome of this study is the percentage uptake of breast cancer screening, three months after the initial invitation letter. This will be reported as both intention-to-treat and per protocol, according to whether the SMS messages were received. Currently it is estimated that the screening service has access to 80% of mobile numbers of invitees.

Secondary outcomes will involve how the uptake differs according to:

- demographics (e.g. ethnicity, deprivation)
- invitation type (open and timed invitation)
- attendance history (previous non-attendee, recurrent attendee, first-time invitee)

We will also repeat the primary analysis to determine the uptake at 6 months. These timepoints were chosen firstly from the literature which suggests the impact of behavioural interventions occurs in the acute decision phase, but also following discussion with the screening service where 6 monthly reporting coincides with a key performance indicator.

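### Section 7 attaches 80% power to 2797 per arm without giving control uptake or sidedness; at 67.3–70% uptake the planned chi-squared test has about 68–70% power for 3 points

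*Combined protocol and SAP*

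**What the plan says.** The only sizing text is in section 7 (Statistics and data analysis). With a 5% type 1 error it gives "80% power, and an effect size of 3%, results in a minimum sample size of 2797 people per study arm", or 8391 in total. The same section names the test: "Chi-squared non-parametric statistic will be used to determine whether effects are significant".

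Section 2 sets the comparisons: "The primary object is to determine the impact of behavioural science informed (1) video and (2) SMS messages compared to usual care". Section 3.1 defines the endpoint: "The primary outcome of this study is the percentage uptake of breast cancer screening, three months after the initial invitation letter".

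No section gives a control uptake at three months, says whether the 5% is one-sided or two-sided, or says whether 3% is an absolute or a relative change. The nearest rates are in section 1.1: "London has shown particularly poor rates (67.3%), with coverage in 2020 below the acceptable target of 70" (per cent). Both are coverage figures.

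**The concern.** The sample size for comparing two proportions depends on the control proportion and on the sidedness of the test. Without them the stated 80% cannot be checked. When the rates in section 1.1 are put in and the test is taken as two-sided, which is what a chi-squared test on a 2×2 table is, 2797 per arm falls well short of 80%.

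This bears on how the result is read. Section 7 presents 3% as a worthwhile effect. If a trial of about this size shows no significant difference, readers will take the risk of having missed such an effect to be 20%, when it may be nearer one in three.

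**Working it through.** **Inputs from the documents.** n = 2797 per arm, type 1 error 5%, effect 3% (section 7); 1:1:1 allocation (section 3).

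**Inputs assumed because the documents omit them.** Effect d = 0.03, in absolute points. Control uptake p1 = 0.673 or 0.70, the two coverage figures in section 1.1. Each intervention arm is compared with usual care (section 2) by a two-sided test at 5%, with no adjustment for making two comparisons.

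**Step 1: reproduce 2797.** The usual unpooled formula is n = (z_α + z_β)² × [p1(1 − p1) + p2(1 − p2)] / d².

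- One-sided 5%, 70% vs 73%: (1.645 + 0.8416)² = 6.183; variance sum 0.2100 + 0.1971 = 0.4071; n = 6.183 × 0.4071 / 0.0009 = 2796.6, rounded up to **2797**.
- One-sided 5%, 67.3% vs 70.3%: 2946.
- Two-sided 5%, 70% vs 73%: (1.960 + 0.8416)² = 7.849; n = 3550 (3554 with pooled variance under the null).
- Two-sided 5%, 67.3% vs 70.3%: 3740 (3743 pooled).

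So 2797 matches a one-sided calculation from the 70% target. A two-sided calculation returns about 2797 only near 78.4% control uptake, or its low counterpart near 18.6%. The total, 3 × 2797 = 8391, is correct.

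**Step 2: power of the planned test at 2797 per arm.** Power = Φ{[d√n − z_α√(2p̄q̄)] / √(p1q1 + p2q2)}, where p̄ is the mean of p1 and p2, q = 1 − p, z_α = 1.960 and d√n = 0.03 × √2797 = 1.5866.

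- p1 = 0.673: (1.5866 − 1.960 × 0.6552) / 0.6549 = 0.462; power **67.8%**.
- p1 = 0.70: (1.5866 − 1.960 × 0.6384) / 0.6380 = 0.526; power **70.0%**.

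A simulation of 400,000 trials with the Pearson chi-squared test gave 67.8% and 70.1%; with Yates' correction, 66.8% and 69.1%.

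**Step 3: dependence on control uptake (two-sided, +3 points, 2797 per arm).**

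| Control uptake | Power |
|---|---|
| 50% | 61.2% |
| 60% | 63.5% |
| 67.3% | 67.8% |
| 70% | 70.0% |
| 75% | 75.4% |
| 78% | 79.4% |

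Power reaches 80% only at about 78.4% or above, or 18.6% or below.

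**Step 4: what 2797 per arm can detect.** Solving for d at 80% power gives 3.46 points at 67.3% and 3.37 points at 70%.

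**Step 5: other readings.**

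- Relative 3%: d is 0.03 × 67.3 = 2.02 points or 0.03 × 70 = 2.10 points, and power is 36.8% or 41.0%.
- Alpha of 2.5% for each of the two comparisons: 57.1% and 59.6%. The plan does not propose this split.
- One overall three-arm chi-squared test (2 degrees of freedom), with one or both intervention arms 3 points higher: about 70–74%.

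**Step 6: larger enrolment (an assumed range; the documents give no expected number).** Two-sided power for 3 points at 67.3% and 70%: 4000 per arm, 82.5% and 84.4%; 5000, 89.9% and 91.4%; 8000, 98.4% and 98.8%.

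**The case against.** Four points can be made for the plan.

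- **2797 is not a slip.** It follows from a coherent one-sided calculation. That is right: the fault lies in unstated inputs and a probable mismatch with the named test. If one-sided testing was intended, section 7 has to say so, because a chi-squared test has no direction and section 2 states none.
- **The baselines are proxies.** The 2020 coverage and the coverage target are not uptake three months after a letter, and invitation type varies during the study: "The decision to offer an individual a timed or open invitation is made by the screening service based on their covid-19 recovery process". This stands, so 68–70% is conditional. It does not rescue the 80%, which needs uptake of about 78% or more (or below about 19%), while section 1.1 describes London rates as poor. If three-month uptake is lower than coverage, though still above about 50%, power is lower again.
- **The form of the chi-squared test is open.** Section 7 does not say pairwise or three-arm, and section 1.2 also mentions video against behavioural SMS. This stands as a further gap, but the three-arm version still gives only 70–74%.
- **2797 is a floor.** This is the strongest point. The study summary defines the population as "All women aged between 50 and 70, invited to screen in the London breast cancer screening region", section 3 randomises everyone due for screening in the study period, and nothing stops enrolment at 8391. The shortfall disappears at 3554 per arm (10,662 in total) if uptake is 70%, or 3743 (11,229) if it is 67.3%. Realised power may well exceed 80%. But section 7 attaches the 80% to the minimum itself and gives no expected number.

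**Conclusion.** The concern holds. The stated 80% power cannot be verified from section 7, and at the only rates the documents offer, the planned test does not deliver it at the stated minimum. Power there is about 68–70% for a 3-point gain, so the risk of missing such a gain is 30–32%; 80% power is reached for about 3.4–3.5 points.

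This rests on reading 3% as absolute points, on control uptake close to 67.3–70%, on two-sided pairwise tests at an unadjusted 5%, and on enrolment near 2797 per arm. That the sizing was one-sided is an inference from the numerical match and is not stated anywhere. The point should be fixed. It does not show that the trial as run will be underpowered, since enrolment may go well beyond the minimum.

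**What to change.** In section 7:

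1. State the sizing inputs: the control uptake assumed at three months and its source, whether 3% is in absolute percentage points, and whether the calculation was one-sided or two-sided.
2. State the analysis separately: which comparisons the chi-squared test makes, at what level, and whether it is two-sided. Two-sided 5% tests of each intervention arm against usual care would fit section 2.
3. Restate power for that test. If control uptake is taken as 67.3–70%, suitable text is: *The minimum of 2797 per arm gives about 68–70% power for a difference of 3 percentage points, or 80% power for about 3.4–3.5 points, with a two-sided 5% chi-squared test of each intervention arm against usual care, unadjusted for the two comparisons.*
4. If more than 2797 per arm are expected, give that number and the power it provides.

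The cost is wording only, and the minimum sample size need not change. The downside is a less favourable power statement at that minimum.

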The content of the intervention messages, and the video have been developed through extensive Patient and Public Involvement and Engagement work including 10 interviews, 2 focus groups and 2 co-design workshops. Members of the public have been consulted throughout the process, especially regarding the representations of individuals in the video, and the message content. The feedback received has been used to alter the materials, and further feedback received. Through this iterative approach we have ensured content is appropriate. We have also sought feedback from members of the Oremi centre (a mental health day service specifically for African Caribbean and Arabic Speaking adults) and Gendered Intelligence (a trans-led organisation to improve the quality of life of trans people) to ensure individuals from these groups are happy with representations. Screening commissioners, led by [name] (NHS England Breast Screening Lead, London), have also approved this content. The NHS Identity team have provided approvals for the use of NHS logos/branding, and the team at London Northwest Healthcare NHS Trust approved the use of their name.

The video will be hosted on a private page on the Imperial College London website, which will be available only to those who have been sent the link. The video will be translated into several languages, with voice overs also available in different languages, to ensure people from a diverse background are able to understand the content.

After 3 months from the initial written invitations, data will be collated from the breast screening hub regarding whether an individual attended an appointment and whether the messages were successfully sent. This will be repeated at 6 months corresponding to the key performance indicator of the service.

Figure 1. Message content for timed and open invitations for the trial arms (a) control, (b) plain text SMS with BCTs and (c) BCT SMS with new link to BCT video.

Reminders at 7 and 2 days prior to appointment		
a) Control	b) Behavioural SMS	c) Behavioural SMS + Video

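### The primary test is an unadjusted chi-squared although ethnicity, reported as strongly linked to attendance, is already extracted; prespecified adjustment would give a modest, cheap gain in precision, provided ethnicity is the pre-invitation value.

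*Combined protocol and SAP*

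**What the plan says.** Section 3.1 defines the endpoint: "The primary outcome of this study is the percentage uptake of breast cancer screening, three months after the initial invitation letter". Section 7 names one test, "Chi-squared non-parametric statistic will be used to determine whether effects are significant", and no covariates. It then assigns regression to the subgroup questions: "A regression model will be developed to test these secondary hypotheses". No adjusted primary comparison is prespecified elsewhere.

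Allocation is unstratified (section 3): "Participants will be randomised using simple randomisation method in a 1:1:1 fashion to either intervention arm or usual care".

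Ethnicity is among the variables listed for extraction in section 7. Section 1.1 cites one London study in which "the adjusted odds of attendance were almost three times higher amongst White British, compared to Asian women, and six times higher than Black women".

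On size, section 7 gives "a minimum sample size of 2797 people per study arm", while the Study Summary describes the population as "All women aged between 50 and 70, invited to screen in the London breast cancer screening region".

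On timing, section 3 says that three months after the invitations "data will be collated from the breast screening hub regarding whether an individual attended an appointment", and section 8.3 says the data come from the NBSS system. Neither section says when ethnicity is recorded.

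**The concern.** Adjusting for a baseline variable that predicts the outcome reduces the variance of the treatment comparison. The plan will already hold such a variable and uses it for subgroup analysis, but leaves it out of the primary test. At the stated minimum size, that forgoes a small amount of power and slightly narrower confidence intervals that need no further participants. If the choice to adjust is made after the results are seen, it is open to challenge, so the decision belongs in the plan now.

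There is also a trap. The extract is taken after attendance is known. If ethnicity is completed or corrected when a woman attends, it is partly a consequence of the outcome, and adjusting for it would distort the comparison.

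**Working it through.** **1. Reproducing 2,797.** Section 7 gives 5% type 1 error, 80% power and a 3% effect, read here as 3 percentage points. It gives neither baseline uptake nor sidedness. With n per arm = (z_a + 0.8416)² × (p0q0 + p1q1) / 0.03²:

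| Uptake | Sides | n per arm |
|---|---|---|
| 70% vs 73% | one | 2,796.6 |
| 70% vs 73% | two | 3,550.3 |
| 78.4% vs 81.4% | two | 2,797.2 |

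The stated figure therefore fits either 70% vs 73% one-sided or about 78.4% vs 81.4% two-sided. Two-sided at 70% vs 73%, 2,797 per arm gives 0.03/√(0.4071/2,797) = 2.487, and Φ(2.487 − 1.960) = 70.1% power.

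**2. Variance explained by ethnicity.** The odds ratios of 3 and 6 come from section 1.1 and are used as if marginal. The White/Asian/Black mixes are assumed, with no other groups. Stratum uptakes p_s are solved so that overall uptake p stays fixed, and R² = Σ w(p_s − p)² / [p(1 − p)].

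For the 55/25/20% mix at p = 0.70, uptake is 82.9%, 61.8% and 44.7%. Then R² = (0.55×0.129² + 0.25×0.082² + 0.20×0.253²)/0.21 = 0.113.

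| Mix (%) | R², odds ratios 3 and 6 | R², log odds ratios halved (1.7 and 2.4) |
|---|---|---|
| 55/25/20 | 0.113 | 0.030 |
| 65/20/15 | 0.109 | 0.028 |
| 75/15/10 | 0.093 | 0.023 |
| 85/10/5 | 0.062 | 0.015 |

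At p = 0.784 the full-odds-ratio values are 0.094, 0.096, 0.087 and 0.061, and the halved values run from 0.024 to 0.013.

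**3. Power at 2,797 per arm.** Power = Φ(0.03/√(V(1 − R²)/n) − z_a), where V = p0q0 + p1q1. For 30% unknown ethnicity, R² is multiplied by 0.7. Example: 2.487/√(1 − 0.113) = 2.640, and Φ(2.640 − 1.960) = 75.2%, a gain of 5.1 points.

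| Basis | Unadjusted power | Gain, complete ethnicity | Gain, 30% unknown |
|---|---|---|---|
| 70/73, two-sided | 70% | 2.7–5.1 | 1.9–3.5 |
| 70/73, one-sided | 80% | 2.2–4.0 | 1.5–2.8 |
| 78.4/81.4, two-sided | 80% | 2.4–3.8 | 1.7–2.7 |
| 70/73, two-sided, log odds ratios halved | 70% | 0.65–1.3 | 0.45–0.9 |

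In participants, R² of 0.062–0.113 is worth 2,797 × 0.062 ≈ 173 to 2,797 × 0.113 ≈ 316 per arm.

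**4. Larger trials** (70/73, two-sided, complete ethnicity).

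| n per arm | Unadjusted power | Gain, full odds ratios | Gain, halved |
|---|---|---|---|
| 5,000 | 91.4% | 1.6–2.8 | 0.4–0.8 |
| 8,000 | 98.8% | 0.4–0.6 | 0.1–0.2 |
| 10,000 | 99.7% | under 0.2 | under 0.1 |

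Confidence intervals narrow by 1 − √(1 − R²) at any size. At 70% uptake this is 3.1–5.8% with complete ethnicity and 2.2–4.0% with 30% unknown. With halved log odds ratios it is 0.7–1.5% and 0.5–1.0%.

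**5. Check with the logistic model itself.** In 100,000 simulated trials per case (70/73, two-sided), adjusted power was 0.752, 0.746, 0.744 and 0.729 across the four mixes. With 30% unknown it was 0.735, 0.732, 0.729 and 0.718. Unadjusted power was 0.698–0.704, and adjusted type 1 error was 0.0495–0.051. The approximation in step 3 is adequate.

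**6. If ethnicity is filled in at attendance.** Ethnicity is assumed unknown for 5% of attenders and for a higher share of non-attenders. The adjusted model is fitted to expected counts with full odds ratios and a true difference of 3.0 points.

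| Unknown in non-attenders | Adjusted difference (points) | Power |
|---|---|---|
| 20% | 2.84–2.86 | 70–72% |
| 40% | 2.43–2.46 | 63–66% |
| 60% | 1.90–1.93 | 53–55% |

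At 40% and 60%, adjustment is worse than the unadjusted 70%.

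**The case against.** The strongest reply is that nothing here is an error. Under simple 1:1:1 randomisation the unadjusted comparison is valid and estimates the percentage uptake that the protocol names. That stands: this is an efficiency point.

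The size of the gain also rests on inputs the documents do not supply: ethnic mix, completeness of recording, baseline uptake and sidedness. The odds ratios come from one study and were already adjusted for other factors. At 2,797 per arm, two-sided 70% vs 73%, the range runs from 0.4 to 5.1 points, and the top needs the most diverse mix, full odds ratios and complete recording together. That stands too, and is why the gain is given as a range. If every London invitee over the study period is randomised, the power gain may vanish. But 2,797 is the only per-arm size the plan commits to.

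A third reply is that adjustment could do harm through late-recorded ethnicity, and that attendance history, which by its meaning precedes the invitation, would be a safer covariate. The harm is real and makes the recommendation conditional. Attendance history is a reasonable addition, but the documents give no strength of association for it, so no gain can be quantified from them. Ethnicity is the only extracted covariate for which they give a figure supporting a useful gain.

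**Conclusion.** The concern holds as a worthwhile improvement to a valid analysis. If the section 1.1 odds ratios apply to invitees and the mix lies between 55/25/20% and 85/10/5%, adjusting for ethnicity at 2,797 per arm adds about 2–5 power points on any of the sizing bases considered with complete recording, and about 1.5–3.5 with 30% unknown. If the association is about half as strong on the log scale, the gain is around 1 point or less. In a trial several times larger, only slightly narrower intervals remain.

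Adjustment does not repair the separate uncertainty about sidedness. If 2,797 came from the one-sided calculation, two-sided power at 70% vs 73% is about 70%, and adjustment lifts it only to about 73–75% at the full odds ratios. All of this depends on ethnicity being a genuine pre-invitation value.

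**What to change.** Before outcome data are seen, amend section 7 as follows:

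- Make the primary analysis of three-month uptake, for each message against usual care, a logistic regression on arm adjusted for ethnicity, with an 'unknown' category.
- Use only the ethnicity value held before the invitation was sent, and say so. If the screening hub cannot supply it, do not adjust for ethnicity.
- Report the standardised risk difference with a 95% confidence interval, so that the result stays on the percentage-uptake scale.
- Keep the unadjusted chi-squared test as a sensitivity analysis.
- Name now any other baseline covariates to be included, such as attendance history, without claiming a quantified benefit from them.

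The cost is SAP wording, minor programming and one question to the hub about when ethnicity is recorded. No extra participants or data fields are needed if the pre-invitation value is available. The hub's answer also bears on the planned ethnicity subgroup analysis, so it is worth having at any sample size.
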